The overall proposed project activities and timeline are shown below. This project has an anticipated on- year timeline.

Table 2. Project Timeline (5/1/2022-4/30/2023) Milestones/Project Activities	Μ	I	J	Α	S	0	Ν	D	J	F	М	Α
winestones/ r roject Activities	IVI	J	J	A	3	U	14	U	J	г	IVI	А
Finalize all materials necessary for the vaccine strategies utilized in the SMART trail	•											
Add additional 3-5 school districts to be eligible for drive-up testing that will begin in May	•											
Obtain IRB Approval	•											
Submit to Clinical Trails.gov	•											
Implement tracking log to implement strategies	•											
Enroll unvaccinated participants from students, staff, and family members that utilized drive-up testing in the vaccine strategy SMART study.		•										
Implement data coordination, collaboration, harmonization w/ RADx-UP CDCC	•	•	•	•	•	•	•	•	•	•	•	•
Conduct monthly superintendent meetings	•	•	•	•	•	•	•	•	•	٠	•	•
Conduct symptomatic testing for all established school districts	•	•	•	•	•	•	•	•	•	•		
Analyze testing data										•	•	
Conduct Listing sessions & Interviews				•	•	•	•					
Conduct Qualitative analysis								•	•			
Share data with Duke coordinating Center	•	•	•	•	•	•	•	•	•	•	•	•
Disseminate result		1								•		•

Study Setting and Populations.

The following school districts in St. Louis County will be included: University City, Ferguson-Florissant, Normandy, Pattonville, St. Louis Language Immersion School, Maplewood-Richmond Heights, and Jennings. Additional schools within the STL County and STL City region will be reached out as potential testing sites. Individuals who are students, staff, and household members of students and staff are eligible to participate in the SARS-CoV-2 testing portion of the study. All St. Louis City and St. Louis County residents along with students, staff, and their household members within the school districts will be eligible for the vaccine uptake trial if they: (1) are not vaccinated (defined as never having received any dose of a COVID-19 vaccine series) but (2) are eligible to receive an approved COVID-19 vaccine.

Testing

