The primary outcome of this study will be the percentage of individuals who received an initial vaccination within two weeks of a study intervention. Vaccine uptake will be primarily assessed by verbal confirmation of recent vaccination during a follow-up visit with a study team member. We will ask for visual documentation of the vaccine card or receipt that demonstrates the vaccine has been administered. Any participants lost to follow-up will be presumed "Unable to determine." A secondary outcome will be the number of individuals that complete their primary vaccination series within 6 weeks of their first dose.

In addition, data from the vaccine-uptake survey will analyzed for trends in willingness to vaccinate within participants. Changes promoting vaccine willingness could be indicative of an impactful vaccine intervention.

E Statistical Plan

Statistical considerations

Primary analysis

Our primary hypothesis is that the initial strategy of peer counseling will result in the highest vaccine uptake. To test this hypothesis we will use a generalized linear mixed model approach, assuming a binomial distribution and a logit link function. The intervention (peer counseling vs SMS + multimedia website) will be modeled as a fixed effect, and household will be included as a random effect to adjust for within household clustering. As this hypothesis focuses on addressing the best initial intervention, we will include only data collected through the first assessment in this analysis (~ 2 weeks following enrollment). If we find a significant difference (P < 0.05) and the proportion of vaccinated participants is greater in the peer counseling group, then we will conclude that the peer counseling is superior to the SMS + video as an initial vaccination strategy. We will also evaluate whether there is evidence of imbalance between the intervention groups for a variety of covariates including: age, race/ethnicity, sex, zip code, school district, highest education level, vaccine hesitancy, influenza vaccine history, previous COVID-19 illness, household member vaccinated, health insurance type, and perceived COVID-19 risk. If we find some evidence of a difference between the initial intervention groups (P <

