0.10) then those variables will be included in the final multivariable model to estimate the adjusted difference between the interventions. If we find no appreciable difference between the adjusted and unadjusted differences, then we will report the unadjusted difference as our primary result.

Secondary analyses

Our secondary analyses will entail analysis of non-responders as well as subgroup analyses. For those that do not respond to the initial intervention, we hypothesize that switching the intervention will result in the greatest vaccine uptake. We will use the same analytic strategy as in the analysis of the primary outcome, with the exceptions that: (1) we will only analyze participants that did not respond to the initial intervention (i.e., non-responders); and (2) we will test the null hypothesis of no difference in the proportion of participants agreeing to a vaccine between those non-responders that switched (peer \rightarrow SMS + multimedia website, SMS + multimedia website \rightarrow peer) compared to those that did not switch (peer \rightarrow Peer, SMS + multimedia website \rightarrow SMS + multimedia website).

For both the analysis of the initial intervention, and the non-responder analysis we will conduct several subgroup analyses. The subgroup analyses will entail analysis of vaccine uptake stratified by: age (<5, 5-11, 12-17, 18 and older), race (white vs black vs other), school district, health insurance, and gender identity. We will use the same analytical approach as previously discussed for the primary and secondary analyses. Results from these subgroup analyses will enable us to determine whether any of these groups modify the effect of vaccine uptake. Furthermore, estimates from these analyses (in addition to the primary analysis) are critical for understanding the factors that potentially modify vaccine uptake and applying results from our studies to other target populations with similar characteristics^{9,10}.

Sample size estimates

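### Subgroup analyses on five factors at both randomisation stages are meant to settle effect modification, but the plan has no interaction test, multiplicity control or exploratory label

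*Combined protocol and SAP*

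**What the plan says.** The Primary analysis part of Section E names one contrast, peer counselling versus SMS plus website at the first assessment, tested in a logit mixed model with a household random effect. Its decision rule begins: "If we find a significant difference (P < 0.05) and the proportion of vaccinated participants is greater in the peer counseling group". No other threshold for a treatment effect is given. The P < 0.10 in the same part concerns baseline imbalance.

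The Secondary analyses part contains the non-responder comparison (switched versus not switched) and the subgroups:

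- **Scope.** "For both the analysis of the initial intervention, and the non-responder analysis we will conduct several subgroup analyses", so there are two stages.
- **Factors.** "age (<5, 5-11, 12-17, 18 and older"), followed by "race (white vs black vs other), school district, health insurance, and gender identity". Age has four levels and race three. Health insurance and gender identity have no levels. The Study Setting part of Section C names seven districts ("University City, Ferguson-Florissant, Normandy, Pattonville, St. Louis Language Immersion School, Maplewood-Richmond Heights, and Jennings") and allows for more.
- **Method.** "We will use the same analytical approach as previously discussed for the primary and secondary analyses". The analyses are described as stratified, and no interaction term appears.
- **Use.** "Results from these subgroup analyses will enable us to determine whether any of these groups modify the effect of vaccine uptake". The next sentence calls the estimates critical, both for understanding modifiers and for carrying results to other populations.

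Sample size estimates powers the trial for the overall peer versus SMS comparison only.

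**The concern.** Two gaps combine. First, many comparisons share an unadjusted threshold, and nothing tells the reader to treat an isolated significant stratum as a lead rather than a finding. Second, a stratified analysis gives a P value within each stratum. Such P values do not show that the effect differs between strata, which is the question the plan says these analyses will answer.

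A team that followed the text exactly could report one district, age band or race group as a modifier and use it to transport the results elsewhere, although the data show only chance variation or unequal stratum sizes.

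**Working it through.** **1. The plan's own figures.** Table 1 under Sample size estimates reproduces with n per arm = (1.96 + 0.8416)² × [p₁(1 − p₁) + p₂(1 − p₂)] / (p₂ − p₁)² and p₁ = 0.036.

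- 5% row: 7.849 × (0.0347 + 0.0786) / 0.0025 = 355.7, so 356 per arm and 712 in total. Then 712 × 1.25 = 890, and 890 / 0.8 = 1112.5, so 1113.
- 12% row: 7.849 × (0.0347 + 0.1317) / 0.0144 = 90.7, so 91 per arm and 182 in total, then 228 and 285.
- The 7% and 9% rows also match. One-sided 0.05 gives 562/328/222/144 and does not fit, so the threshold is two-sided 0.05.

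The plan states no family-wise error rate for the subgroups.

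**2. Number of tests.**

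- One test per factor per stage: 5 × 2 = 10.
- One test per stratum, from levels in the documents: (4 + 3 + 7) × 2 = 28.
- Adding an assumed minimum of two levels each for insurance and gender identity: (14 + 2 + 2) × 2 = 36.

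**3. Chance of at least one two-sided P < 0.05 with no effect anywhere.** For k independent tests this is 1 − 0.95^k. The correlated columns come from 200,000 draws of equally correlated normal statistics.

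| Tests | Independent | Correlation 0.25 | Correlation 0.5 |
|---|---|---|---|
| 10 | 40% | 37% | 29% |
| 28 | 76% | 67% | 49% |
| 36 | 84% | 75% | 55% |

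A large-sample simulation with factors independent of one another, so that strata overlap as they would in one set of participants, gave 41% for 10 interaction tests, 73% for 28 stratum tests and 80% for 36. Independent tests pass one half at 14 (51.2%; 13 give 48.7%).

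**4. Favoured direction only.** The primary rule also requires the result to favour peer counselling. At 0.025 per test, 10 tests give 22% if independent and 14% at correlation 0.5. An omnibus interaction test over three or more levels has no direction, so this range applies only to single-contrast tests.

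**5. Sparse data.** This simulation used 38 stratum tests (levels 4, 3, 7, 3, 2), assumed stratum shares, no household clustering and 3.6% uptake in both arms. Wald tests with a zero cell counted as non-significant.

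| Evaluable N | Score | Likelihood ratio | Wald |
|---|---|---|---|
| 228 | about 40% | about 74% | 1–2% |
| 890 | about 75% | 90–92% | 31–33% |

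**6. If peer counselling works equally everywhere.** Take the 5% row: 80% power with 712 independent participants, so the expected statistic is 1.96 + 0.84 = 2.80. Seven equal districts (assumed) each have 2.80 / √7 = 1.06, which gives power P(Z > 1.96 − 1.06) ≈ 18%. The chance that no district is significant is 0.816⁷ ≈ 24%, and that all seven are is negligible. So in about 76% of trials some districts would be significant and others not, although the effect is the same in all. This is a normal approximation. With about 51 per arm in each district, expected events are only 51 × 0.036 = 1.8 and 51 × 0.086 = 4.4.

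**The case against.** The case against has four parts.

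- **The plan does have an order.** It names one primary hypothesis, powers the trial for it alone, and puts the subgroups under secondary analyses. The subgroup tests do not affect the error rate of the primary test. Leaving secondary subgroups unadjusted is common, and the text also speaks of estimates and of potential modifiers. All of this stands. A reader might infer that the primary conclusion is compromised, or that a subgroup could establish efficacy; the documents support neither.
- **P < 0.05 is not restated for subgroups.** It is inferred from the shared analytic approach. That is correct, but no other treatment-effect threshold is available to apply.
- **A false claim is not shown to be more likely than not.** A reader might draw that conclusion from five factors at two stages. Those are 10 tests, and 10 tests give at most about 40%. A majority needs a test in every stratum, and even then it depends on correlation, test, sample size and uptake; Wald tests at the smallest sample almost never reject.
- **If peer counselling works, a significant stratum is not a false positive.** This is right, and adjusting stratum P values would not cure the resulting error. It shows that an interaction test is needed as well as multiplicity control.

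What survives is that the section assigns these analyses the task of determining modification and gives no method that can do it.

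**Conclusion.** The point holds as a gap in status and method. The size is as follows.

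- About 29–40% for 10 tests under the global null, or 14–22% if only results in the favoured direction count.
- About 49–84% for 28 to 36 stratum tests that hold nominal size, over correlations 0 to 0.5.
- With sparse events the stratum-level figure ranges from near zero (Wald, smallest sample) to about 90% (likelihood ratio, largest sample), so no single figure should be quoted as the trial's risk.

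These rest on assumptions that the documents do not supply: the levels of insurance and gender identity, the stratum shares, the correlations between tests and, in the sparse-data runs, no household clustering. The absence of an interaction test, an adjustment and an exploratory label rests on the text alone. So does the conclusion that within-stratum P values cannot establish modification. The primary analysis is untouched, and this is a cheap improvement.

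**What to change.** In Section E:

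1. State that peer versus SMS at the first assessment is the only confirmatory test.
2. Label all subgroup analyses at both stages exploratory. Report stratum estimates with 95% confidence intervals and draw no conclusion from within-stratum P values.
3. Assess modification by one treatment-by-factor interaction test per factor per stage, and define the levels of each factor, including insurance and gender identity. If any modifier is to be claimed, apply Holm across these 10 tests; the smallest P value would then have to fall below 0.05 / 10 = 0.005.
4. Reword the sentence "Results from these subgroup analyses will enable us to determine whether any of these groups modify the effect of vaccine uptake" so that the results are explored for modification and are not said to determine it.

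Making the non-responder switch test conditional on the primary result is optional and not needed here.

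The cost is SAP wording only, with no new data or participants and no loss of alpha for the primary test. The downside is that an isolated subgroup P < 0.05 can no longer be presented as an established modifier.

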We powered this study to test the primary hypothesis that an initial intervention of peer counseling will result in greater vaccine uptake compared to the SMS + multimedia website intervention. The sample size needed to test this hypothesis was based on pilot data as well as scientific literature on vaccination uptake. One research study estimated an increase COVID-19 vaccine uptake rate of 3.6% with a text reminder treatment compared to a holdout arm that did not receive a reminder^{11C}. Our listening session data from our community members, felt that receiving vaccination information from a peer would be helpful in becoming vaccinated. Additionally, peer counseling has been noted to increase breastfeeding rates in different race/ethnicity groups of at least 15%. For this reason, we estimate that 15% of participants will agree to a vaccine after having a conversation with a peer. Pilot data available for the study population indicated that the median household size was 1, and for the power analysis we assume 1 person per household but in the main analyses we will include a random effect to account for possible clustering at the household level if there is greater than one person per household. The aforementioned estimates from the literature served as our targets, but due to the inherent uncertainty in the application of results from prior studies to different target populations, we estimated the necessary sample sizes for a range of vaccine uptake-rates (Table 1). Based on these estimates we anticipate that a total drop-out adjusted sample size (peer counseling, SMS + multimedia website) ranging from 285 (increase in vaccine uptake of 12%) to 1113 (increase in vaccine update of 5%) would provide a minimum of 80% power to detect the

effect of interest. These sample sizes are attainable as we already have approximately 1000 unvaccinated individuals that we can contact for enrolment. Additionally, we will be adding more school districts to be eligible for testing. Lastly, we will recruit for enrollment beyond just testing as we utilize our community partners to help us with recruitment.

Increase in % uptake of vaccine	Total sample (unadjusted for drop out)	Total sample size + design effect*	Total sample (adjusted for 20% drop out)			
5%	712	890	1113			
7%	416	520	650			
9%	282	353	442			
12%	182	228	285			

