Table 1. Sample size estimates for different scenarios comparing the peer intervention to the SMS + multimedia website intervention. All scenarios assume 80% power and a 3.6% vaccine uptake rate for SMS + multimedia website based on results from Dai et al. 2021. *Design effect assumes an intracluster correlation of 0.50 and an average cluster size of 1.5.

Data management

All testing data are maintained in a secure, password-protected REDCap database. Information collected on paper forms is stored in locked filing cabinets on a restricted-access floor at WUSM. Prior to undergoing testing, participants will complete a HIPAA authorization form and/or informed consent to allow SARS-CoV-2 testing data to be shared with the State of Missouri. All participants are assigned an ID number, and testing information is kept separate from the demographic data. Subjects who test positive are contacted by phone to be given their results. This information will be shared only with the participant unless an informed consent is signed that will allow sharing of their data with the RADx-UP Coordination and Data Collection Center.. Data are stored using HIPAA-compliant encryption to comply with all local, state, and national regulations for health-related data.

Our existing Consortium Data Reporting Unit (CDRU), in collaboration with our data manager, will coordinate the submission of common data element metrics on SARS-CoV-2 testing-related outcomes to the RADx-UP CDCC at Duke University. We will comply with data sharing as mandated by the NIH and follow guidance provided by the CDCC for data acquisition, collection, and curation, including appropriate consent for data sharing and implementation of the schemas proposed under the ABOUT ML effort. The CDRU will also ensure compliance with federal, state, and local requirements and policies for testing, reporting, and surveillance. The CDRU will also work closely with the CDCC to employ a common set of tools to promote collection of comparable data on social determinants of health, including measures from the PhenX Toolkit. Effective implementation strategies for rapid adoption will be disseminated through the CDCC.

We will work collaboratively with the Duke CDCC in reviewing and revising our data collection tools to ensure we are collecting the appropriate CDEs. We will share our data with Duke

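### The logit mixed model fitted within each school district will often give no finite odds ratio at the plan's own 3.6% SMS uptake, except perhaps at the largest planned total

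*Combined protocol and SAP*

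**What the plan says.** The subgroup paragraph of section E (Secondary analyses) covers both the initial-intervention analysis and the non-responder analysis. It lists five stratifying factors: age in four bands, and "race (white vs black vs other), school district, health insurance, and gender identity". The method is given in one sentence: "We will use the same analytical approach as previously discussed for the primary and secondary analyses". For the primary analysis, section E states that "we will use a generalized linear mixed model approach, assuming a binomial distribution and a logit link function", with intervention as a fixed effect and household as a random effect. The plan expects the subgroup results to show whether these factors modify the effect, and regards the estimates as essential for carrying the findings to other populations.

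Section C (Study Setting and Populations) names seven districts: "University City, Ferguson-Florissant, Normandy, Pattonville, St. Louis Language Immersion School, Maplewood-Richmond Heights, and Jennings". The project timeline foresees 3 to 5 more. City and county residents outside any district may also enrol in the vaccine trial. On sample size, the note to the table in section E says: "All scenarios assume 80% power and a 3.6% vaccine uptake rate for SMS + multimedia website". Planned totals run from 285 participants for a 12-point increase to 1113 for a 5-point increase.

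The plan gives no minimum stratum size or event count, no rule for pooling strata, no sparse-data method and no intervention-by-subgroup test.

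**The concern.** A logit model needs at least one vaccinated and one unvaccinated participant in each arm to give a finite odds ratio. If nobody in a stratum's SMS arm is vaccinated while the peer arm has both outcomes, the data are quasi-completely separated. The likelihood then has no finite maximum for the intervention effect, and the Wald P value has no meaning. A household random effect does not cure this, and neither does an ordinary, unpenalised intervention-by-district interaction, because the empty cells remain.

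With SMS uptake assumed at 3.6%, the analysed sample divided among at least seven districts and then between two arms leaves very few events per cell. At stake is whether a named set of analyses, on which the plan relies for effect modification and transport to other populations, can be delivered by the stated method. If it cannot, the replacement method would be chosen after seeing which strata converged.

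**Working it through.** **Inputs from the document.** SMS uptake 3.6%; increases of 12, 9, 7 and 5 points; 80% power; P < 0.05; design effect from an intracluster correlation of 0.50 and mean cluster size 1.5; 20% drop-out; seven named districts.

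**Assumptions.** 1:1 allocation (the ratio is not stated), a two-sided test, seven equal districts, every participant belonging to one of them, and 20% drop-out removed.

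**Step 1: the plan's sample sizes.** Total = 2 × ceil[(p₁q₁ + p₂q₂)(1.96 + 0.8416)²/d²]. For 12 points: (0.036 × 0.964 + 0.156 × 0.844) × 7.849/0.0144 = 90.7, so 91 per arm and 182 in total. The other rows give 282, 416 and 712. The design effect is 1 + 0.5 × 0.50 = 1.25, giving 228, 353, 520 and 890. Dividing by 0.8 gives 285, 442, 650 and 1113. Every figure in the plan's table is reproduced.

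**Step 2: events per district.** Per district and arm, n = N/14. Expected SMS events = 0.036n. P(no SMS event) = 0.964ⁿ. P(no peer event) = (1 − p₂)ⁿ. P(either arm empty) = 1 − (1 − P_SMS)(1 − P_peer), multiplied by 7 for the expected number of districts.

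| Analysed N (peer uptake) | n | Expected SMS events | P(no SMS event) | P(no peer event) | Districts of 7 with an empty arm | Chance of at least one |
|---|---|---|---|---|---|---|
| 228 (15.6%) | 16.3 | 0.59 | 55% | 6.3% | 4.1 | 99.8% |
| 353 (12.6%) | 25.2 | 0.91 | 40% | 3.4% | 2.9 | 98% |
| 520 (10.6%) | 37.1 | 1.34 | 26% | 1.6% | 1.9 | 89% |
| 890 (8.6%) | 63.6 | 2.29 | 10% | 0.3% | 0.7 | 52% |

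The plan's own target of 15% against 3.6% is a difference of 11.4 points, nearest the first row. With no drop-out at all (285 to 1113 analysed), expected SMS events per district are 0.73 to 2.86.

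**Step 3: household clustering.** Assume half the households have one member and half have two (mean 1.5), with correlation 0.50. In a two-person household, P(neither vaccinated) = 0.964² + 0.5 × 0.036 × 0.964 = 0.9466. P(no SMS event in a district) = (0.964 × 0.9466)^(½ × n/1.5), which gives 61%, 46%, 32% and 14%.

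**Step 4: more districts.** If the 3 to 5 districts are additional to the seven, the step 2 formula gives 7.1 (N = 228) to 2.1 (N = 890) of 10 districts with an empty arm, or 9.2 to 3.4 of 12.

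**Step 5: other strata.** For k equal strata, P(at least one with no SMS event) = 1 − (1 − 0.964^(N/2k))^k. At the four totals, four age strata give 82%, 59%, 32% and 7%; three race strata give 58%, 31%, 12% and 1%.

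**Step 6: non-responder analysis.** The contrast is switch against no switch, so each side mixes peer and SMS recipients. Assume stage-2 rates equal stage-1 rates and take their simple average: 9.6%, 8.1%, 7.1% and 6.1%. Expected non-responders are (N/2)(0.964 + 1 − p₂) = 206, 324, 483 and 836, or 14.7, 23.2, 34.5 and 59.7 per district and side. With P₀ = (1 − average rate)ⁿ, 7 × [1 − (1 − P₀)²] gives about 2.8, 1.8, 1.1 and 0.3 districts with an empty side.

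**The case against.** The strongest case on the other side limits the scope of the point, and most of it stands.

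- **Not every total is affected.** A reader might infer that many district odds ratios fail throughout the planned range. At 890 analysed with seven equal districts the expected number is 0.7, and there is roughly an even chance (48%) of none.
- **Not every subgroup is affected.** Three race strata are largely safe at the larger totals. Insurance and gender identity cannot be assessed, because the plan does not give their categories.
- **The two stages differ.** A reader might carry the first-stage figures over to the non-responders. Step 6 shows that contrast is milder, because neither side sits at 3.6%.
- **The 3.6% is uncertain.** The sample-size text describes it as an increase over a no-reminder arm, while the table uses it as the SMS uptake itself. If uptake were 8% (an assumption), 7 × 0.92ⁿ gives 1.8, 0.9, 0.3 and 0.03 districts with an empty SMS arm.
- **Stronger technical claims are not supported.** An empty SMS arm does not by itself make the household variance inestimable, since multi-person households in the peer arm remain. Nothing in the plan says that strata without convergence would be dropped, so selective reporting cannot be inferred.

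It could also be said that stratifying need not mean separate fits. However, the sentence on method makes fitting within strata the natural reading, and an unpenalised interaction meets the same empty cells. Nor does the plan call these analyses exploratory. The gap therefore remains: on the plan's own rate, the stated method often fails for districts, and no fallback is given.

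**Conclusion.** The point holds for school district at the small and middle totals, including the row nearest the plan's own target, where more than half of the seven districts would have no finite odds ratio. At 890 analysed it is a moderate risk, though about 2.3 expected SMS events still cannot support a stable district odds ratio. Age strata share the problem at the smaller totals; race strata and the non-responder contrast share it to a lesser degree.

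The figures rest on the 3.6% rate, 1:1 allocation, seven equal districts, everyone belonging to a district, and 20% drop-out. Unequal or additional districts, residents outside any district, and household clustering all make the cells sparser. Higher SMS uptake would ease the problem.

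A reader might take this as a fault in the main result. It is not: the primary test, its sample size and its conclusion rule are untouched.

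**What to change.** Revise the subgroup paragraph of section E as follows.

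- For every stratum, report n, the number vaccinated per arm and the difference in percentages. This matches the primary outcome, which is itself a percentage. Use an interval that is defined at zero events and allows for household clustering, for example a score interval on sample sizes reduced by the design effect, or a household bootstrap where events allow.
- Do not use separate per-district logit mixed models for inference.
- Assess effect modification in one model on all participants with an intervention-by-subgroup term, fitted with a penalised (Firth-type) or otherwise shrunken estimator and accounting for household.
- Label the district results descriptive.

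Two apparent shortcuts should be avoided. A minimum of five events per arm would suppress nearly every district: at 3.6%, the chance that a district's SMS arm reaches five is about 0.02% at 228, 1% at 520 and 8% at 890. A model with a freely estimated random intervention slope by district is likely to be singular at the smaller totals, since the whole SMS arm expects only 114 × 0.036 = 4.1 events at 228.

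The cost is SAP wording, with no change to enrolment, data collection or the primary analysis. The downside is small: district results carry no separate P value, and shrunken estimates are pulled toward the overall effect.

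### The plan says its subgroup analyses will determine effect modification, but it includes no interaction term or other test that compares the intervention effect between subgroups

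*Combined protocol and SAP*

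**What the plan says.** The subgroup plan is one paragraph in section E, Secondary analyses, of the combined protocol and SAP.

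- **Scope.** "For both the analysis of the initial intervention, and the non-responder analysis we will conduct several subgroup analyses".
- **Factors.** "The subgroup analyses will entail analysis of vaccine uptake stratified by: age (<5, 5-11, 12-17, 18 and older), race (white vs black vs other"), followed by "school district, health insurance, and gender identity". Age has four levels and race three. Levels for insurance and gender identity are not given. The Study Setting section names seven districts and allows more.
- **Method.** "We will use the same analytical approach as previously discussed for the primary and secondary analyses". The Primary analysis section describes that approach as a binomial mixed model with a logit link, in which the intervention "will be modeled as a fixed effect, and household will be included as a random effect to adjust for within household clustering". Covariates that look imbalanced between arms may be added, but only as adjustment terms.
- **Claim.** "Results from these subgroup analyses will enable us to determine whether any of these groups modify the effect of vaccine uptake". I take this to mean modification of the intervention's effect on uptake. The next sentence calls the estimates critical for applying the results to other populations.

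No interaction term, heterogeneity test or rule for comparing strata appears anywhere in the document. The sample size section powers the primary hypothesis only.

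**The concern.** Effect modification is a difference between stratum-specific effects. Fitting the treatment model within a stratum estimates that stratum's effect and tests it against zero. It does not test one stratum's effect against another's, so a set of such fits cannot determine modification, whatever the individual results.

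With no stated method of comparison, the easiest way to read the output is to note which strata reach significance. In a trial sized for one overall comparison, that pattern depends heavily on stratum size and chance. What is at stake is a statement that a racial, age or district group does or does not respond to peer calls, which the plan intends to carry over to other populations.

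**Working it through.** **Inputs from the plan.** SMS uptake 3.6%; peer uptake 15% in the text; increases of 5 to 12 points, 80% power and 20% dropout in the sample size table; intracluster correlation 0.50 and mean cluster size 1.5 in the table note. **Assumptions.** Two-sided 0.05, 1:1 allocation, equal strata, independent participants at the effective sample size.

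**1. Reproduce the plan's sample sizes.** n per arm = (1.960 + 0.842)² x [p1(1−p1) + p2(1−p2)] / d².
- +5 points: 7.849 x (0.0347 + 0.0786) / 0.0025 = 355.7, so 356 per arm and 712 in total. Design effect 1 + 0.5 x 0.50 = 1.25, and 712 x 1.25 = 890. Then 890/0.8 = 1112.5, so 1113.
- +12 points: 7.849 x (0.0347 + 0.1317) / 0.0144 = 90.7, so 91 per arm and 182 in total. Then 182 x 1.25 = 227.5, so 228, and 228/0.8 = 285.

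Both rows match the table.

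**2. Effective size per stratum.** Effective N = N x 0.8/1.25.
- N = 285 gives 182.4. Over three race strata and two arms this is about 30 per arm per stratum.
- N = 1113 gives 712.3. Over four age strata and two arms this is about 89 per arm per stratum.

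**3. Chance of a mixed pattern when every stratum has the same effect.** With power w in each of K strata, P(some but not all significant) = 1 − w^K − (1−w)^K. The plan names no test statistic, so three are shown, with w from exact enumeration of the two binomial distributions.

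| Setting | Test | w | Mixed pattern |
|---|---|---|---|
| Race, K = 3, N = 285, 15% vs 3.6% | Wald (log odds) | 0.063 | 18% |
| | Fisher | 0.128 | 34% |
| | Chi-square | 0.349 | 68% |
| Age, K = 4, N = 1113, 8.6% vs 3.6% | Wald (log odds) | 0.188 | 56% |
| | Fisher | 0.185 | 56% |
| | Chi-square | 0.267 | 71% |

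For example, race by Wald is 1 − 0.063³ − 0.937³ = 0.18. Simulation gave 18%, 34% and 69% for race and 58%, 58% and 72% for age, so the last digit should not be relied on. The 285 row of the table is for 15.6% rather than 15%. Using 15.6% raises the race range slightly, to 21% (Wald, w = 0.074) and 70% (chi-square, w = 0.375).

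**4. What a between-strata test would do.** In simulation with the same uptake rates in every stratum, a Cochran Q test on log odds ratios rejected in 0.2% of trials for three strata at effective N = 182 (15.6% vs 3.6%) and in 1.1% for four strata at effective N = 712. The maximum over 2, 3, 4 and 7 strata was about 4%. These rates are below 5% because the counts are sparse, which also signals low power.

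**5. Sparseness by district.** With seven equal districts, expected SMS-arm vaccinations per district are 285 x 0.8/14 x 0.036 = 0.6, or 1113 x 0.8/14 x 0.036 = 2.3. A separate mixed model within a district could barely be fitted at either size.

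**The case against.** Several points on the other side have force.

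- **The plan does not say that modification will be judged by which strata reach P < 0.05.** A reader might infer that it does. The only P < 0.05 decision rule concerns peer against SMS as the initial strategy, and the subgroup paragraph also speaks of estimates and of factors that might modify uptake. Comparing estimates by eye is an equally open reading. This narrows the point but does not remove it, because no method of comparing estimates is given either.
- **A large false-positive rate is tempting to infer but not supported.** One could count at least 18 strata (4 + 3 + 7 + 2 + 2), compute 1 − 0.95^18 = 60%, and 1 − 0.95^36 = 84% over both analyses. That assumes independent tests at full 5% size and two levels each for insurance and gender identity, which the plan does not state. The factors divide the same participants, and tests on sparse counts fall below 5%. Simulating 18 strata with no effect, the chance of at least one P < 0.05 in the initial analysis was about 0.1% to 20% at N = 285 and 16% to 54% at N = 1113, depending on the test. Those two percentages should not be used.
- **The mixed-pattern figures depend on the test.** This stands, and is why ranges are given.
- **The analyses are secondary, and an interaction test would be weak.** Both are true. The primary conclusion is unaffected, and neither approach is likely to settle modification in strata this small. But the plan does not label the analyses exploratory, and it claims they will determine modification.

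**Conclusion.** The point holds in this form: the plan promises a conclusion about effect modification that its stated method does not provide, because nothing in it compares the intervention effect between strata. This follows from the text alone and needs no numerical assumption.

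The figures only show how misleading stratum-by-stratum reading could be. With no modification at all, a mixed pattern of significance arises in roughly one trial in five to two in three for race at N = 285, and in more than half of trials for age at N = 1113. They assume equal strata, no clustering beyond the 1.25 design effect, two-sided tests and 1:1 allocation. They do not show that the sponsor will declare false modifiers. This should be corrected, but it does not threaten the primary analysis.

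**What to change.** Replace the by-stratum refits in Secondary analyses with the following.

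- For each factor, and separately for the initial and non-responder analyses, fit one model to all participants in that analysis. Include the intervention (or switch versus no switch), the subgroup factor, their interaction and the household random effect. One model also keeps together households whose members fall in different age groups.
- Base any statement about effect modification on the interaction test, taken jointly over levels where there are more than two, and on the confidence interval for the interaction. Name the test statistic.
- Report stratum estimates with confidence intervals, descriptively only.
- State the levels of insurance and gender identity, and pool sparse levels such as districts by a rule set before outcomes are seen by arm.
- Label the results exploratory, and replace the claim to determine modification with one to explore it.

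The cost is about one paragraph of wording and no new data. The downside is low power: fewer modifiers will be declared, and the text should say that a non-significant interaction is not evidence of a uniform effect.
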